### 9.1.1 Deaths, Serious and Adverse Events Leading to Early Study Drug Termination

The listings of deaths, SAEs, AEs leading to study drug discontinuation, and AEs of special interest will be provided.

## 9.2 Clinical Laboratory Parameters

Laboratory assessments include hematology, clinical chemistry, and urinalysis:

- Hematology: Hemoglobin, Hematocrit, Erythrocytes, Leukocytes + differential, Thrombocytes (platelet count).
- Clinical Chemistry: Total Bilirubin, Aspartate Aminotransferase (AST), Alanine Aminotransferase (ALT), Blood Urea Nitrogen (BUN), Glucose, Potassium, Sodium, Calcium, Alkaline Phosphatase, Chloride, Creatinine, Carbon Dioxide (CO2), eGFR.
- Urinalysis: pH, Color, Clarity, Specific Gravity, Urobilinogen, Ketones, Protein, Glucose, Bilirubin, Blood, Leukocyte esterase, Nitrite

All laboratory parameters will be presented in SI units. Quantitative results (including actual value, and change from baseline) will be summarized using descriptive statistics by baseline and post-baseline visit for each laboratory test group above. Laboratory test results will be assigned an LNH classification according to whether the value was below (L), within (N), or above (H) the normal reference range (some urinalysis labs are assigned only normal and abnormal classifications). Values outside the normal range are also classified as to whether they were potentially clinically significant (PCS). The number and percentage of subjects in each category will be summarized by baseline and post-baseline visit for each lab test. In addition, shift tables cross-tabulating the baseline and post-baseline LNH classifications, by visit, will be provided. The PCS criteria are:

Clinical Chemistry	Hematology	Urinalysis
Total Bilirubin $\geq 1.5x$ ULN	Hemoglobin $< 0.85x$ LLN or $>1.25x$ ULN	pH $\leq 4$ or $>9$
AST (SGOT) $\geq 3x$ ULN	Hematocrit $< 0.85x$ LLN or $>1.25x$ ULN	Color N/A
ALT (SGPT) $\geq 3x$ ULN	Erythrocytes $< 0.85x$ LLN or $>1.25x$ ULN	Clarity N/A
BUN $\geq 1.5x$ ULN	Leukocytes + differential (total) $< 0.50x$ LLN or $>1.50x$ ULN	Specific Gravity $< 1.001$ or $> 1.035$
Glucose $< 0.8x$ LLN or $>1.5x$ ULN	Thrombocytes (platelet count) $< 0.50x$ LLN or $>1.50x$ ULN	Urobilinogen $> 4.0$ mg/dL
Potassium $< 0.9x$ LLN or $>1.1x$ ULN		Ketones positive value if negative pre-Rx or $\geq 2$ unit increase from pre-Rx

Sodium < 0.95x LLN or >1.05x ULN		Protein positive value if negative pre-Rx or $\geq 2$ unit increase from pre-Rx
Calcium < 0.9x LLN or >1.1x ULN		Glucose positive value if negative pre-Rx or $\geq 2$ unit increase from pre-Rx
Alkaline Phosphatase $\geq 1.5x$ ULN		Bilirubin positive value if negative pre-Rx or $\geq 2$ unit increase from pre-Rx
Chloride < 0.9x LLN or >1.1x ULN		Blood positive value if negative pre-Rx or $\geq 2$ unit increase from pre-Rx
Creatinine $\geq 1.5x$ ULN		Leukocyte esterase positive value if negative pre-Rx or $\geq 2$ unit increase from pre-Rx
CO2 < 0.8x LLN or >1.2x ULN		Nitrite positive value if negative pre-Rx or $\geq 2$ unit increase from pre-Rx
eGFRc < 0.8 x LLN (LLN=90, regardless of calculation method)		

All laboratory data will be included in the listings. A pregnancy listing will be provided separately.

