2. STUDY OBJECTIVES AND PURPOSE

2.1. Rationale for the Study

Cyclin-dependent kinase-like 5 (CDKL5) deficiency- mediated early-onset infantile epileptic encephalopathy is a rare genetic disorder with approximately 1,600 documented cases worldwide ([Loulou Foundation](#)). The CDKL5 gene is on the X chromosome; consequently, the condition affects mainly girls, although boys can also be affected. The CDKL5 gene produces a protein that is important for neuronal morphogenesis and brain development, ([Fuchs et al., 2014](#)) and helps regulate expression of genes involved in synaptic function, structure, and plasticity ([Carouge et al., 2010](#); [Kameshita et al., 2008](#)).

Cyclin-dependent kinase-like 5 deficiency disorder is characterized by early-onset intractable seizures, severe developmental delay, disturbed sleep and severe intellectual/gross motor impairment ([Bahi-Buisson et al., 2008](#)). Typically, the seizures are resistant to conventional antiepileptic medication. Treatment-resistant epilepsy can be fatal and patients are often treated with high doses of multiple AEDs that worsen the cognitive, behavioral and physical consequences of the underlying disorder. Together, these children and young adults experience major impairments to quality-of life. Any therapy that can reduce the frequency, duration or severity of seizures can positively impact quality of life for the child and family ([Müller et al., 2016](#)).

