4.1. Inclusion Criteria

The subject will not be considered eligible for the study without meeting all the criteria below.

1. (a) Molecular confirmation of a pathogenic or likely pathogenic CDKL5 variant, early onset, difficult to control seizures, and neurodevelopmental impairment are required. The principal investigator (PI) must review the results of the genetic analysis and confirm that gene mutation is likely to be the cause of the epilepsy syndrome. If the patient has a *de novo* variant of unknown significance (VUS) in the kinase domain of the CDKL5, parental testing is negative and meets all other inclusion criteria, then the subject can be included. Genetic mutations will be confirmed by the sponsor's chosen central laboratory. In France, genetic mutations may be confirmed by an approved French organization, in compliance with French legislation prior to Screening Visit 1. Patients must have (b) seizure onset by 1 year of age and (c) lack of independent ambulation by 2 years of age.
2. Male or female patients aged 2 through 21 years, inclusive.
3. Subject/parent or LAR willing to give written informed consent/assent, after being properly informed of the nature and risks of the study and prior to engaging in any study-related procedures.
4. Failure to control seizures despite appropriate trial of 2 or more anti-seizure medications at therapeutic doses
5. Have at least 16 seizures of primary seizure types: bilateral tonic (sustained motor activity ≥ 3 seconds), generalized tonic-clonic, bilateral clonic, atonic/drop or focal to bilateral tonic-clonic per 28 days in each 1-month period in the 2-month period prior to screening.
6. Subject must be approved to participate by sponsor and/or designee (i.e., Epilepsy Consortium) after review of medical history, genetic testing, seizure classification, and historical seizure calendars.
7. Participants should be on a stable regimen of 0-4 anti-seizure medications (including moderate or strong inducer or inhibitor anti-seizure medications e.g. carbamazepine, phenytoin, etc.) for ≥ 1 month prior to the screening visit, without a foreseeable change in dosing for the duration of the double-blind phase. Vagus nerve stimulator (VNS), ketogenic diet, and modified Atkins diet do not count towards this limit but must be unchanged for 3 months prior to screening.
8. Subjects with surgically implanted VNS will be allowed to enter the study provided that all of the following conditions are met:

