10. Have any disease or condition (medical or surgical; other than CDKL5) at screening that might compromise the hematologic, cardiovascular, pulmonary, renal, gastrointestinal, or hepatic systems; or other conditions that might interfere with the absorption, distribution, metabolism, or excretion of the investigational product, or would place the subject at increased risk.
11. An AST (serum glutamic oxaloacetic transaminase [SGOT]) or ALT (serum glutamic pyruvic transaminase [SGPT]) greater than 3 times the upper limit of normal (ULN) at study entry. If AST or ALT increases > 3 times ULN during the study, subject should be followed with weekly laboratory repeat testing and continue in study if levels trending down. Subject will be discontinued if levels do not decline to under 3 x ULN.
12. Total bilirubin levels greater than ULN at study entry. In cases of documented, stable medical condition (i.e., Gilbert's Syndrome) resulting in levels of total bilirubin greater than ULN, the medical monitor can determine if a protocol exception can be made. If total bilirubin increases to 1.5 x ULN or more during study, the subject will be discontinued.
13. Subjects with significant renal insufficiency, estimated glomerular filtration rate (eGFR) < 30 mL/min (calculated using the Cockcroft-Gault formula, Pediatric GFR calculator or Bedside Schwartz), will be excluded from study entry or will be discontinued if the criteria is met post baseline.
14. Have been exposed to any other investigational drug within 30 days or less than 5 half-lives prior to screening.
15. Unwillingness to withhold grapefruit, Seville oranges or star fruit from diet during the entire clinical trial.
16. Unwillingness to withhold alcohol throughout the entire clinical trial.
17. Have active suicidal plan/intent or have had active suicidal thoughts in the past 6 months or a suicide attempt in the past 3 years.
18. Known sensitivity or allergy to any component in the investigational product(s), progesterone or other related steroid compounds.

19. Plasma allopregnanolone – sulfate (Allo-S) levels ≥ 6.0 ng/ml at the screening visit.

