7.6.5. Clinical Laboratory Tests

Laboratory safety assessments will be collected at every clinic visit throughout the study to monitor subject safety. Clinical laboratory tests are listed in [Section 12.2](#) will be collected per the schedule listed in [Table 1](#) and [Table 2](#). These clinical laboratory assessments will include CBC with automated differential, creatinine, blood urea nitrogen, and eGFR calculation, comprehensive metabolic panel, as well serum pregnancy test for all women of childbearing potential.

The following liver function and eGFR tests will be monitored throughout the study as follows.

- If AST or ALT increases > 3 times ULN during the study, subject should be followed with weekly laboratory repeat testing and continue in study if levels trending down. Subject will be discontinued if levels do not decline to under 3 x ULN.
- If total bilirubin increases to 1.5 x ULN or more during study, the subject will be discontinued.

- Subjects with significant renal insufficiency, eGFR < 30 mL/min (calculated using the Cockcroft-Gault formula or Pediatric GFR calculator or Bedside Schwartz) will be discontinued if the criterion is met post baseline.

If any of the criteria above are deemed clinically significant by the investigator, then the sponsor's medical monitor should be contacted.

Due to the difficulty in obtaining urine samples, urinalysis will be conducted at Visit 1 (screening) or baseline (Visit 2), Week 17 (Visit 5), Week 52 (Visit 9), and annually thereafter or at the safety follow up visit if investigational product is discontinued. An attempt will be made to collect a urine sample at screening in order to perform the study-related urinalysis. Otherwise, the urine sample for the urinalysis can be collected at baseline.

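### SAP 9.2 applies one eGFR limit to formulas on different scales, so if Cockcroft-Gault is used in young children the renal flag can depend on the formula

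*SAP*

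**What the plan says.** Exclusion criterion 13 (Protocol 4.2) lets eGFR be "calculated using the Cockcroft-Gault formula, Pediatric GFR calculator or Bedside Schwartz". Protocol 7.6.5 repeats the three options for on-study monitoring: "calculated using the Cockcroft-Gault formula or Pediatric GFR calculator or Bedside Schwartz) will be discontinued if the criterion is met post baseline". Both passages give the threshold as 30 mL/min, without indexing to body surface area. Neither says which subjects get which method, nor that a subject keeps the same method.

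eGFR is a scheduled safety parameter: 7.6.5 lists "creatinine, blood urea nitrogen, and eGFR calculation, comprehensive metabolic panel". SAP 9.2 puts it in the chemistry panel, which is summarized by visit as value, change from baseline, Low/Normal/High (L/N/H) and PCS counts, and L/N/H shift tables. It adds: "Values outside the normal range are also classified as to whether they were potentially clinically significant (PCS". The eGFR criterion itself is "eGFRc < 0.8 x LLN (LLN=90, regardless of calculation method", with no unit and no age adjustment.

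The population is "Male or female patients aged 2 through 21 years, inclusive" (Protocol 4.1), and "the condition affects mainly girls, although boys can also be affected" (Protocol 2.1).

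**The concern.** Cockcroft-Gault gives an absolute clearance in mL/min that is proportional to body weight, with a reduction factor for females. Bedside Schwartz gives a value per 1.73 m² that is proportional to height. The two are on similar numerical scales in an adolescent or adult but not in a small child. One fixed limit therefore need not define the same event under both, and the SAP wording explicitly sets the difference aside.

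At stake is whether the eGFR rows of the safety tables can be read. A Low or PCS count could partly reflect formula and body size, and a change of formula within a subject would appear as a change in renal function. The SAP uses age-specific ranges for vital signs (9.3.1) and for PR and QRS (9.3.2), so the flat eGFR limit departs from its own practice.

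**Working it through.** **The plan's figure.** 0.8 × 90 = 72. Below 90 is Low; below 72 is Low and PCS.

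**Assumptions.** The documents name the formulas but print no equations, so the standard forms are assumed:

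- Cockcroft-Gault = (140 − age) × weight / (72 × creatinine), × 0.85 in females, in mL/min.
- Bedside Schwartz = 0.413 × height / creatinine, in mL/min per 1.73 m².

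Weight is in kg, height in cm, creatinine in mg/dL. Sizes and creatinine values are also assumptions; two sets of sizes are used.

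**Ratio of the scales.** Creatinine cancels. In girls, Cockcroft-Gault / Schwartz = (140 − age) × weight × 0.85 / (72 × 0.413 × height):

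- Age 2, 11 kg, 85 cm: 138 × 11 × 0.85 / (29.736 × 85) = 0.51. At 12 kg, 87 cm it is 0.54.
- Age 4, 15 kg, 101 cm: 0.58. At 16 kg, 102 cm it is 0.61.
- Age 8, 25 kg, 127 cm: 0.74.
- Age 14, 45 kg, 157 cm: 1.03.

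**Single cases.**

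- Girl, 2 years, 12 kg, 87 cm, creatinine 0.30. Cockcroft-Gault: 138 × 12 × 0.85 / (72 × 0.30) = 65.2, PCS. Schwartz: 0.413 × 87 / 0.30 = 119.8, normal.
- Same girl at 0.20: 97.8 and 179.7, both normal.
- Boy of the same age and size at 0.35: 65.7 (PCS) and 102.7 (normal).
- Girl, 4 years, 0.35. At 15 kg, 101 cm: 68.8 (PCS) and 119.2 (normal). At 16 kg, 102 cm: 73.4 (Low, not PCS) and 120.4 (normal).

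**Where the two disagree.** PCS by Cockcroft-Gault requires creatinine above (140 − age) × weight × 0.85 / (72 × 72), without the 0.85 in boys. Normal by Schwartz requires creatinine of at most 0.413 × height / 90. For a 2-year-old girl of 12 kg and 87 cm the bounds are 1407.6 / 5184 = 0.27 and 35.93 / 90 = 0.40.

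| Age | kg / cm | Girls, mg/dL | Boys, mg/dL |
|---|---|---|---|
| 2 | 12 / 87 | 0.27–0.40 | 0.32–0.40 |
| 3 | 14 / 95 | 0.31–0.44 | 0.37–0.44 |
| 4 | 16 / 102 | 0.36–0.47 | 0.42–0.47 |
| 5 | 18 / 109 | 0.40–0.50 | 0.47–0.50 |
| 6 | 20 / 115 | 0.44–0.53 | 0.52–0.53 |
| 8 | 25.5 / 128 | 0.55–0.59 | none |
| 10 | 32 / 138 | none | none |

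**Sensitivity to weight.** For the 2-year-old girl, 20% less weight gives 0.22–0.40 and 20% more gives 0.33–0.40. The age at which the range closes also moves: a 10-year-old girl at 25.6 kg (20% below 32) has a lower bound of 130 × 25.6 × 0.85 / 5184 = 0.55 and an upper bound of 0.413 × 138 / 90 = 0.63, so a range reopens.

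**Change of method.** If the 2-year-old girl at a constant 0.30 had Schwartz at baseline and Cockcroft-Gault later, her change would be 65.2 − 119.8 = −54.6, a Normal-to-Low shift and a new PCS value, with creatinine unchanged.

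**Unit.** Indexing her Cockcroft-Gault value, with body surface area = √(12 × 87 / 3600) = 0.54 m², turns 65.2 into about 209. The missing unit alone can change the class.

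**The 30 mL/min passages.** On the first-listed sizes, a Cockcroft-Gault value of 30 in a girl corresponds to a Schwartz value of about 30 / 0.51 = 59 at age 2 and 30 / 1.03 = 29 at age 14. The same stated figure is thus not the same quantity under the permitted methods.

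**The case against.** The strongest reply is that no passage says Cockcroft-Gault will be used in small children. It is listed beside two pediatric options for a population aged 2 to 21, and choosing by age is a natural reading. That stands: a reader might infer that many young subjects would be flagged at baseline and at every visit, but the documents do not support this. The result is conditional on the method and on size, sex and creatinine. The 4-year-old example changes class with 1 kg and 1 cm, and typical sizes and creatinine may not suit children with this disorder.

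A reader might also infer that all three formulas disagree. Only two can be compared; the pediatric calculator is undefined and could itself be a Schwartz equation. Nor do the documents say that methods change between visits. If one laboratory uses one method throughout, no switching artefact arises, but nothing requires that.

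Finally, it is tempting to say that a real renal signal would be hidden or a false difference between arms created. SAP 9.2 separately flags creatinine and BUN at 1.5 × ULN or more, summarizes both by visit and lists all laboratory data. Method choice should be unrelated to arm under blinding. On the 30 mL/min rule, Protocol 4.5.2 allows continued treatment when a criterion 11–13 abnormality is not medically significant, and nothing shows that any subject would be near the threshold.

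What survives is the stated SAP rule: it anticipates more than one method and applies one limit to all.

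**Conclusion.** The point holds in conditional form. Three methods are permitted, none is assigned or held fixed, and one limit applies to all. Under the standard equations, Cockcroft-Gault and Bedside Schwartz differ by a factor of about two in 2-year-old girls and agree by about age 14. If Cockcroft-Gault is used in young children, some will be PCS by it and normal by Schwartz, within the creatinine ranges tabulated above.

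The consequence is confined to descriptive tables: eGFR change from baseline, L/N/H, PCS and shifts. The primary efficacy test is untouched and no bias by arm is claimed. The documentary part is certain; the numbers rest on assumed equations, sizes and creatinine values. The change is worth making because this is a pediatric safety table and the remedy is cheap.

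**What to change.** In SAP 9.2:

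- Delete the clause that makes the eGFR limit independent of the method.
- Derive eGFR centrally from the collected creatinine and the latest height, with one named equation indexed to 1.73 m²: Bedside Schwartz, which is already permitted, for pediatric subjects, and one pre-named indexed equation for adult subjects.
- Fix the equation within subject by age at baseline, and state the age cut and the unit.
- Apply LLN = 90 and the PCS limit only to the derived value; keep reported eGFR in the listings.

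The cost is one SAS derivation from data already collected, plus SAP wording. There are two drawbacks. Height is measured at screening and then not until Week 34 (Protocol 7.6.2), so screening height is carried forward through the double-blind phase. Height may also be imprecise in non-ambulant subjects or those with scoliosis.

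Separately, the sponsor must reconcile the formula and unit in exclusion criterion 13 and Protocol 7.6.5 with the stated eGFR < 30 mL/min. No threshold is proposed here.

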### 9.3 Other Safety Endpoints

#### 9.3.1 Vital Signs

Vital signs include weight (kg), height (cm), temperature (°C), systolic and diastolic blood pressure (mmHg), respiration rate (breaths per minute), and pulse rate (bpm).

Quantitative results (including actual value, and change from baseline to each post-baseline visit) will be summarized using descriptive statistics by baseline and post-baseline visit for each parameter.

Vital sign test results will be assigned an LNH classification according to whether the value was below (L), within (N), or above (H) the normal reference range. Values outside the normal range will also be classified as to whether they were potentially clinically significant (PCS). Vital signs normal ranges are:

Age	SBP (mm Hg)	DBP (mm Hg)	Pulse (beats/min)	Respiration Rate (breaths/min)
1 – 3 yrs	90-105	55-70	80-125	20-30

> 3 – 6 yrs	95-110	60-75	70-115	20-25
> 6 – 12 yrs	100-120	60-75	60-100	14-22
> 12 yrs	100-120	70-80	60-100	12-18

The subjects’ age categories will be determined by their age at the time of the vital signs collection. Since only the birth years of the subjects are available, the month and day of birth will be assumed July 1st. The subjects’ age at the time of the collection will then be derived as:  $\text{Floor}((\text{Collection Date} - \text{Birth Date} + 1) / 365.25)$ .

PCS abnormalities are defined as:

**SBP:**

High:  $\geq 1.5 \times \text{ULN}$ ; or a  $\geq 20$  mmHg increase from baseline if clinically significant at baseline  
 Low:  $\leq 0.75 \times \text{LLN}$ ; or a  $\geq 20$  mmHg decrease from baseline if clinically significant at baseline

**DBP:**

High:  $\geq 1.3 \times \text{ULN}$ ; or a  $\geq 15$  mmHg increase from baseline if clinically significant at baseline  
 Low:  $\leq 0.70 \times \text{LLN}$ ; or a  $\geq 15$  mmHg decrease from baseline if clinically significant at baseline

**Pulse:**

High:  $\geq 1.20 \times \text{ULN}$ ; or a  $\geq 15$  bpm increase from baseline if clinically significant at baseline  
 Low:  $\leq 0.80 \times \text{LLN}$ ; or a  $\geq 15$  bpm decrease from baseline if clinically significant at baseline

**Respiratory Rate**

Low:  $\leq 0.80 \times \text{LLN}$   
 High  $\geq 1.25 \times \text{ULN}$

The number and percentage of subjects with abnormalities will be summarized by baseline and post-baseline time point for each parameter.

A subject listings of vital signs, including out of the normal range and PCS flags, will be provided.

**9.3.2 ECG**

The 12-lead ECG parameters including value and change from baseline will be summarized using descriptive statistics by baseline and post-baseline visit. Except for QTc, the parameters will be assigned an LNH classification according to whether the value was below (L), within (N), or above (H) the normal reference range. Values outside the normal range, and the QTc parameters, will also be classified as to whether they were potentially clinically significant (PCS).

ECG normal ranges and PCS criteria are:

**HR:** Same as in Vital Signs  
**PR interval:** PCS: < 0.9xLLN or >1.1 x ULN  
**QRS:** PCS: >1.1x ULN  
**QTc B/FN interval:** PCS: ≥ 470 msec (females), ≥ 450 msec (males), or increase ≥ 60 msec from baseline

**PR, QRS Normal Ranges:**

Age	PR Interval (sec)	QRS Duration (sec)
1–3 yr	0.10–0.14	<= 0.07
4–5 yr	0.11–0.15	<= 0.08
6–8 yr	0.12–0.16	<= 0.08
9–11 yr	0.12–0.17	<= 0.09
12–16 yr	0.12–0.17	<= 0.10
>16 yr	0.12–0.20	<= 0.10

Overall ECG results were interpreted as normal, abnormal (not clinically significant) or abnormal (clinically significant). The number and percentage of subjects in each category will be summarized by baseline and post-baseline visit, and shift tables cross-tabulating the baseline and post-baseline ECG interpretations, by visit, will be provided.

A subject listing of the ECG parameters and overall interpretation, including out of the normal range and PCS flags, will be provided.

**9.3.3 Physical, Neurological, and Developmental Examinations**

Physical examination results are interpreted as normal, abnormal (not clinically significant) or abnormal (clinically significant). Neurological examination results were interpreted as normal or abnormal. The number and percentage of subjects in each category for these examinations will be summarized. The developmental examination consists of several questions and the number and percentage of subject replies to each question will be summarized. Listings for all the examinations will be provided.

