7.6.3. Physical/Neurological/Developmental Examinations

The full physical examination will include the following systems:

- General appearance
- Head (eyes, ears, nose and throat)
- Cardiovascular
- Respiratory
- Gastrointestinal
- Genitourinary
- Musculoskeletal
- Endocrine/Metabolic
- Hematologic/lymphatic
- Skin
- Other systems as appropriate

The full neurological examination will include:

- Cranial nerves
- Motor exam
- Sensory exam
- Reflexes
- Coordination/Cerebellar

The full developmental examination will include:

- Speech/language
 - Makes identifiable sounds for specific objects/people
 - Repeats sounds
 - Single words
 - Multiple words
 - Makes a sentence
 - Replies to question in an identifiable sound, single word, multiple word, sentence
 - Other abilities
- Motor
 - Sits with support
 - Sits independently

- Crawls
- Stands with support
- Stands independently
- Takes steps with assistance
- Walks independently
- Other abilities
- Social
 - Smiles appropriately to situation
 - Makes eye contact

Follow up physical, neurological, and developmental examinations are abbreviated examinations that ask whether there have been clinically significant changes or new abnormalities in the subject's physical, neurological, and developmental examinations since the last full examination.

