**9.3.4 Tanner Staging**

This endpoint is a safety endpoint for only the OLE period of the study.

The Tanner scale (also known as the Tanner stages) is a scale of physical development in children, adolescents and adults. The scale defines physical measurements of development based on external primary and secondary sex characteristics. Subjects will be evaluated and rated as

Tanner I, Tanner II, Tanner III, Tanner IV and Tanner V. Tanner staging will occur at Screening (Visit 1), Visit 9 (Week 52) and will continue to be assessed annually for the duration of the subject's participation in the open-label phase and at the final OLE visit.

The number and percentage of subjects of each category will be summarized by Screening and OLE visit, and a listing will be provided.

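### The planned neurological, height and Tanner summaries are insensitive to worsening, although data already collected would support better ones

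*SAP*

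**What the plan says.** **Neurological examination.** SAP 9.3.3 states that "Neurological examination results were interpreted as normal or abnormal" and then that "The number and percentage of subjects in each category for these examinations will be summarized". It names no cross-tabulation against baseline and no category for worsening. The physical examination in the same paragraph has a clinical-significance grade; the neurological examination does not. For the overall ECG reading, SAP 9.3.2 promises that "shift tables cross-tabulating the baseline and post-baseline ECG interpretations, by visit, will be provided", and SAP 9.2 plans the same for laboratory classes.

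**Follow-up examinations.** Protocol 7.6.3 describes abbreviated examinations that "ask whether there have been clinically significant changes or new abnormalities" since the last full one. Tables 1 and 2 place them at Visit 2, Visit 4 (Week 9), Visit 6 (Week 19) and the post-taper safety visit. SAP 9.3.3 names no table for the answers.

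**Developmental examination.** This is handled by item: "The developmental examination consists of several questions and the number and percentage of subject replies to each question will be summarized".

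**Height and weight.** SAP 9.3.1 treats them as vital signs in cm and kg: "Quantitative results (including actual value, and change from baseline to each post-baseline visit) will be summarized using descriptive statistics". Its age-specific ranges cover blood pressure, pulse and respiration only.

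**Tanner stage.** SAP 9.3.4 makes it a safety endpoint of the open-label phase only: "The number and percentage of subjects of each category will be summarized by Screening and OLE visit", plus a listing.

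**The concern.** Protocol 4.1 sets this entry condition: "early onset, difficult to control seizures, and neurodevelopmental impairment are required". It also requires that the child was not walking independently by age 2. Protocol 1.1 describes severe hypotonia and severely impaired psychomotor development. In such a population a subject already classed as abnormal stays abnormal however much the examination deteriorates, so the count cannot move for that subject.

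Height and pubertal stage have a different problem. Subjects are aged 2 to 21, so many will grow and mature during roughly three years of open-label treatment whatever the drug does. Without a control arm or an age and sex reference, a raw mean rise in height or a drift towards later Tanner stages has nothing to be compared with.

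The questions matter. Ganaxolone is a neurosteroid analogue acting on GABA-A receptors, Protocol 1.2 reports that CNS events appeared dose related, and Protocol 8.3.1 makes reproductive and breast disorders events of special interest.

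**Working it through.** SAP 9.3.1, 9.3.3 and 9.3.4 give no figure to reproduce. The arithmetic below shows how far the planned forms can respond.

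**1. Ceiling in the neurological count**

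Inputs:
- n = 50 per arm, from 100 subjects randomised 1:1 (SAP 1.3.2). As a check, 50 per arm with SD 44.5 and a difference of 30 gives power 0.921, against the stated 92%.
- Share abnormal at entry, s: an assumption, shown as a range.
- True worsening in one arm, w = 20% (10 of 50): an assumption, taken as equally likely in subjects normal and abnormal at entry.

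Formulas:
- Subjects able to move from normal to abnormal = n × (1 − s).
- Expected number seen to move = w × n × (1 − s).
- Most extreme contrast: all who can move do so in one arm and none in the other, giving 50 v 50·s abnormal. Fisher's exact two-sided p is used only as a yardstick, since no safety test is planned.

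| s | Able to move | p at most extreme contrast | Expected to be seen, of 10 who worsened |
|---|---|---|---|
| 80% | 10 | 0.001 | 2.0 |
| 90% | 5 | 0.056 | 1.0 |
| 94% | 3 | 0.24 | 0.6 |
| 96% | 2 | 0.49 | 0.4 |
| 98% | 1 | 1.0 | 0.2 |
| 100% | 0 | 1.0 | 0 |

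At about 90% or more, even the most extreme outcome could not stand out. At 80% it could, although some dilution remains (20% × 10 = 2.0 seen of 10). The table assumes one overall call per subject. Protocol 7.6.3 lists five neurological components, and SAP 9.3.3 does not say whether results are overall or by component. A by-component table would leave more room, with motor and coordination the likeliest to sit at the ceiling.

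**2. What the follow-up question covers**

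Full examinations are at screening, Week 5 and Week 17. The Week 9 follow-up asks about change since the last full examination, which is Week 5. Worsening during titration that was already present at Week 5 would not be captured by the Week 9 answer. A shift from the screening examination to Weeks 5 and 17 would capture it, so the two tables complement each other.

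**3. Height and Tanner timing**

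- Height (Protocol 7.6.2): screening, Week 34, Week 52, then annually and at the final visit.
- Tanner (SAP 9.3.4): screening, Week 52, then annually and at the final visit.
- Weight (Protocol 7.6.2): screening and Week 17, then open-label visits.

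The double-blind phase ends at Week 17. Apart from subjects who leave without entering the extension, post-baseline height and Tanner values are therefore all open-label, where SAP 1.2.5 itself urges caution because there is no control arm.

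Illustration, assuming normal growth of 4 to 8 cm a year: slowing by 25% gives 0.75 × 4 = 3 cm to 0.75 × 8 = 6 cm. The slowed range (3 to 6) overlaps the normal range (4 to 8), and both are rises. A raw mean change across ages 2 to 21 cannot separate them.

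**The case against.** The strongest reply is that these tables are not the main instrument for detecting harm.

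- **Adverse events.** Protocol 8.1.1 requires worsening of a pretreatment event to be recorded as a new adverse event, and Protocol 8.1.4 does the same for significant worsening of disease symptoms. SAP 9.1 tabulates these by arm, severity and relationship, with separate treatment for reproductive and breast events.
- **Developmental items.** Sitting, standing, walking, speech and social items are each tabulated, so functional loss can show without a normal/abnormal ceiling.
- **Listings** are planned for all examinations.

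All of this stands. A reader might infer that the plan cannot show neurological or developmental harm; the documents do not support that. What remains is that adverse event capture depends on someone judging a change to be an event, and a listing gives no comparison between arms.

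The ceiling is also an inference. A reader might take near-universal abnormality as documented, but no percentage is stated, and the argument is strong only at about 90% or more.

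A reader might also put weight with height. That would be wrong: Week 17 weight change is summarised by randomised arm, and randomisation balances expected growth.

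Finally, the safety endpoint lists in SAP 1.2.4 and 9 name weight but not height, and no growth objective is visible in the unredacted text. That limits how much weight the growth point should carry. It does not make a raw height change interpretable.

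**Conclusion.** The point holds as one of insensitivity. The neurological count is likely to respond little to worsening, because most subjects probably enter as abnormal. With 50 per arm, 5 subjects or fewer could change category if 90% or more are abnormal at entry. This rests on that assumed share and on a single overall call per subject. Scheduled height and Tanner summaries cannot separate a drug effect from ordinary development, because they have neither a control arm nor an age and sex reference. Week 17 weight is unaffected. The issue is minor: other routes to a signal exist, and the better tables use data already being collected.

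**What to change.** - **SAP 9.3.3:** tabulate, by arm and visit, the subjects answering yes to the follow-up question on change or new abnormality. Add a shift table by neurological component from the screening full examination to each later full examination.
- **SAP 9.3.4:** present Tanner stage as a within-subject shift from screening, by sex. Show age in broad bands or leave it to the listing, because cells will be small.
- **SAP 9.3.1:** add age- and sex-standardised z-scores for open-label height and weight. Age can use the SAP's existing 1 July birth-date convention without rounding down to whole years. State the resulting error: 181 days back to 1 January and 183 days forward to 31 December, so up to about six months. Use age in months instead if it can be obtained.

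**Cost:** SAP wording and extra programming, with no added subject procedure. Obtaining age in months would also need a data collection change, since only birth year is held.

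**Limits:** Tanner cells will be small, reference norms may fit non-ambulant children with CDD imperfectly, and the open-label phase will still have no concurrent control.
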